7.3.1.1. Main Estimand Analysis

The estimand of ORR, with its 5 attributes and the strategies for addressing the defined intercurrent events, is presented in Table 5.

Table 5: Estimand of Objective Response Rate

Estimand Attribute		Definition		
Treatment	Tafasitamab in combination with LEN administered for up to 12 cycles in total, after which participants can continue with tafasitamab as monotherapy.			
Population		All participants with R/R DLBCL as per eligibility criteria who received at least 1 dose of tafasitamab and 1 dose of LEN		
Variable	ORR			
Intercurrent events	Event	Strategy	Rationale (if needed)	
	No postbaseline response assessment or not adequately assessed (eg, NE)	Hypothetical strategy	Participant will be considered as nonresponder	
	Treatment discontinuation due to any reason	Treatment policy	All responses will be considered regardless of treatment discontinuation	
	Death without postbaseline assessment or not adequately assessed (eg, NE)	Hypothetical strategy	Participant will be considered as nonresponder	
	Start of any NALT	While on treatment strategy	Only response prior to the start of any new antilymphoma therapies will be considered	
	Study withdrawal due to any reason during the post-treatment disease follow-up	While on treatment strategy	All responses will be considered up to study withdrawal	
Population-level summary	Percentage and 95% CI us	sing the Clopper-Pearson n	nethod	

7.3.1.2. Summaries

The number and percentage of participants with CR, PR, SD, PD, or NE as the best response will be summarized.

Analysis of ORR will be conducted on the FAS, based on INV assessment according to the IWG treatment response criteria for malignant lymphoma (Cheson et al 2007). The following rules will apply:

- Participants with a best response of NE will be summarized by reason for having a nonevaluable status. The following reasons will be used:
 - No postbaseline assessment available.
 - All postbaseline assessments have overall response NE as indicated by the INV.
 - NALT started before first evaluable postbaseline assessment.
- No formal hypothesis testing will be conducted.

Listings for tumor response assessments will be generated based on the ENR with inclusion in the FAS and PPS noted.

Swimmer plots will be generated showing per participant disease response assessments including disposition events (eg, EOT, AEs, death), best overall response, prior lines of therapy, refractoriness, and NALTs in the same graph.

7.3.1.3. Sensitivity Analysis

The ORR endpoint will be analyzed using the PPS as a sensitivity analysis to the FAS.

7.3.2. Endpoint: Progression-Free Survival

Progression-free survival is defined as the time (in months) from the date of the first administration of any study drug to the date of tumor progression or death from any cause. The date of progression will be the first date for which PD was assessed as the objective response. The analysis will be based on tumor assessments by the INVs according to the IWG treatment response criteria for malignant lymphoma (Cheson et al 2007).

7.3.2.1. Disease Assessments

Disease assessments will be performed with PET-CT, PET-MRI, CT, or MRI scans as per the schedule in Table 3 of the Protocol.

7.3.2.2. Censoring Rules

If a participant is alive and progression-free at the date of the analysis (ie, data cutoff date), the participant will be censored, and the reason for censoring will be provided as per Table 6.

The date of last adequate tumor assessment is the date of the last tumor assessment with an overall response different from NE and not missing before an event or censoring occurred.

Table 6: Censoring Rules for the Progression-Free Survival Estimand

Situation	Date of Progression or Censoring	Outcome	Censoring Reason
Ongoing and no event at data cutoff date	Date of last adequate tumor assessment (ie, not NE and not missing) prior to data cutoff date	Censored	Ongoing
No baseline tumor assessment	Date of Cycle 1 Day 1	Censored	No baseline tumor assessment
No valid postbaseline assessments	Date of Cycle 1 Day 1	Censored	No postbaseline assessments
Progression documented between scheduled response assessments	Date of first response of PD	Progressed	NA
Study withdrawal without documented progression	Date of last adequate tumor assessment (ie, not NE and not missing) prior to data cutoff date	Censored	Study withdrawal
Participant received NALT	Date of last adequate tumor assessment (ie, not NE and not missing) with no documented progression on/before start of NALT	Censored	NALT started

Table 6: Censoring Rules for the Progression-Free Survival Estimand (Continued)

Situation	Date of Progression or Censoring	Outcome	Censoring Reason
Death without prior PD response assessment	Date of death	Progressed	NA
Death between response assessments	Date of death	Progressed	NA
PD with missing assessment date	Date of last adequate tumor assessment (ie, not NE and not missing)	Censored	Date of disease progression missing
Death or progression after 2 or more missed assessments	Date of last tumor assessment with documented nonprogression (ie, CR, PR, or SD)	Censored	Event documented after 2 or more consecutive missed/inadequate tumor assessments

The censoring reasons indicated in Table 6 will be summarized for all time-to-event endpoints. The reason of study withdrawal will be further summarized according to the reasons reported in the "End of Study/Early Follow-Up Discontinuation" eCRF.

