#### ***10.3.2.3 Progression-Free Survival by Investigator Assessment (Secondary Endpoint)***

PFS is defined as the time from the date of randomization to the date of the first radiologically documented disease progression or death due to any cause. If a patient has not progressed or died at the analysis cut-off date or when he/she receives further anti-neoplastic therapy, PFS will be censored on the date of the last adequate tumor evaluation before the earlier of the cut-off date or start of the further antineoplastic therapy date.

Kaplan Meier plots will be used to estimate the distribution of PFS. The PFS probabilities and the associate 95% CI will be summarized.

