4.1.9. Handling of Missing and Incomplete Dates

In general, values for missing dates will not be handled unless methods for handling missing dates are specified in this section or relevant sections. The original reported dates collected in the eCRF should be used in all relevant listings. The following rules will be used for handling partial dates for analyses requiring dates.

When the date of the last dose is used in deriving variables such as duration of treatment or TEAE flag, a missing or partial date of the last dose will be handled as follows:

- If only the day is missing, then the earlier date of the last day of the month or the date that the participant discontinued treatment will be used.
- If both the month and day are missing, then the earlier date of 31 DEC of the year or the date that the participant discontinued treatment will be used.
- Otherwise, the date that the participant discontinued treatment will be used as the date of the last dose.

For relevant efficacy endpoints, a partial date of the death date will be handled as follows in the calculation:

- If mmyyyy for the last known alive date = mmyyyy for the death date, then the death date will be set to the day after the last known alive date.
- If mmyyyy for the last known alive date < mmyyyy for the death date, then the death date will be set to the first day of the death month.
- Otherwise, the partial death date will not be imputed.

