7.3.2.5. Sensitivity Analysis

The following sensitivity analyses for the PFS endpoint will be performed:

- A PFS event occurring after 2 or more missed assessments will be considered an event and back-dated to the date of the next scheduled assessment.
- The PPS will be used as a sensitivity analysis to the FAS.

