7.3.3.1. Censoring Rules

The censoring rules for DoR will be the same as those for PFS (see Table 6).

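### SAP Table 6 censors a progression that is documented but undated, which biases PFS and DoR upward whenever the row is used

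*SAP*

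**What the plan says.** In SAP 7.3.2.2, Table 6 has a row headed "PD with missing assessment date". The participant is censored at the last adequate assessment, with the reason "Date of disease progression missing". SAP 7.3.3.1 extends this to response duration: "The censoring rules for DoR will be the same as those for PFS (see Table 6".

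The related text reads as follows:

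- The sentence introducing Table 6 sets the condition for censoring: "If a participant is alive and progression-free at the date of the analysis".
- Protocol 10.3.2.3 sets it this way: "If a patient has not progressed or died at the analysis cut-off date", or when further antineoplastic therapy is given.
- SAP 7.3.2 defines PFS as running "to the date of tumor progression or death from any cause".
- SAP 4.1.9 states: "In general, values for missing dates will not be handled unless methods for handling missing dates are specified in this section or relevant sections". It then gives rules for last-dose dates and for partial death dates, but none for a tumor-assessment date.
- SAP 7.3.2.5 plans two PFS sensitivity analyses. One is "A PFS event occurring after 2 or more missed assessments will be considered an event and back-dated" to the next scheduled assessment; the other repeats the analysis on the PPS. For DoR, SAP 7.3.3.3 plans only the PPS repeat.

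**The concern.** A participant in this row is known to have progressed. Kaplan-Meier censoring gives that person the later risk of those still progression-free, which is exactly what the record rules out. The censoring is caused by the event, so it is informative, and on average it acts in one direction: towards longer PFS and DoR.

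At stake is the accuracy of two of the three efficacy summaries. DoR is the more exposed, because it is estimated in responders only and each event carries more weight.

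**Working it through.** **1. Consistency of the row with the rest of the plan.** Undated PD does not meet the condition in the Table 6 lead-in, because the participant is not progression-free. It does not meet either condition in Protocol 10.3.2.3, because the patient has progressed and has not necessarily started other therapy. It does meet the event definition in SAP 7.3.2. Table 8 lists no intercurrent event or strategy for it, so the PFS estimand does not support the row.

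**2. Whether another analysis corrects it.** The back-dating analysis in SAP 7.3.2.3 and 7.3.2.5 covers only events after two or more missed assessments. Table 2.2.1.2 in Appendix A (change in censoring) has no other definition in the body text. The PPS analyses keep the same censoring rules. Nothing restores the event.

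**3. Ceiling by algebra.** The plan states no figure to reproduce. Let n be the number at risk at the scan that finds the PD, d the number of PDs at that scan, and S the estimate just before it.

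- Counted as an event: S × (n − d)/n.
- Under Table 6, the undated case leaves the risk set earlier: S × (n − d)/(n − 1).
- With no other censoring, S = n/51, so the difference is (n − d)/(51 × (n − 1)). This is at most 1/51 = 2.0 points and is reached when d = 1.
- The 51 is the approximate enrolment in Protocol section 1, used as an upper bound for the FAS. For 29 responders the same ceiling is 1/29 = 3.4 points.

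At a later time the gap is the event-counted estimate at that time divided by (n − 1). For a PD found with all 51 at risk and a 12-month estimate of 52.1%, it is 52.1/50 = 1.0 point. A PD found after month 12 adds nothing to the 12-month estimate, so the average per case is lower still.

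**4. Average size by simulation.** This was a single-arm Kaplan-Meier simulation with 600 trials per setting.

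- From the documents: the protocol scan schedule (before C3D1, C5D1, C7D1 and C10D1, then C12D28, then about 3-monthly, then yearly from Cycle 25), follow-up of 36 months, and N=51 for PFS.
- Assumed: exponential times with medians of 6, 12 or 24 months; 80% of events being PD; the stated number of undated PDs.
- For DoR: 29 responders, from the 57.5% response rate that the protocol reports for the L-MIND trial (0.575 × 51 = 29.3), with the scan schedule counted from first response as a simplification.

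12-month event-free estimate in %, PD counted as an event → Table 6 rule (differences taken before rounding):

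| Endpoint | Assumed median | 1 undated PD | 2 undated PDs |
|---|---|---|---|
| PFS, N=51 | 6 months | 27.5 → 28.1 (+0.6) | 27.0 → 28.2 (+1.2) |
| PFS, N=51 | 12 months | 52.1 → 52.7 (+0.7) | 52.5 → 53.9 (+1.4) |
| PFS, N=51 | 24 months | 72.3 → 73.0 (+0.7) | 72.1 → 73.5 (+1.4) |
| DoR, n=29 | 6 months | 27.4 → 28.5 (+1.1) | 27.2 → 29.4 (+2.2) |
| DoR, n=29 | 12 months | 52.7 → 54.0 (+1.3) | 52.6 → 55.2 (+2.6) |
| DoR, n=29 | 24 months | 72.5 → 73.7 (+1.2) | 72.4 → 74.9 (+2.4) |

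Five cases, as an extreme, gave +3.3 to +3.7 points for PFS and +5.9 to +6.6 for DoR.

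Kaplan-Meier medians moved little at assumed medians of 6 and 12 months (at most 0.2 months, except DoR with five cases, 14.0 to 15.8). At 24 months the typical PFS median went from 30.7 to 35.0 months with one case. That is a jump to the yearly scan: (336 + 4 × 91 + 365)/30.4375 = 35.0. It reflects sparse late scans rather than a smooth bias.

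**5. Scale.** Ignoring censoring before month 12, the 95% half-width at 52.1% with N=51 is 1.96 × √(0.521 × 0.479/51) = 13.7 points. For DoR at 52.7% with n=29 it is 1.96 × √(0.527 × 0.473/29) = 18.2 points.

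**6. Sensitivity to the date chosen.** Counting the PD at the last adequate assessment, the earliest possible date, lowers the 12-month estimate by at most 0.2 points (PFS) or 0.3 points (DoR) for one case, and by at most 1.0 or 1.6 points in any setting run. An imprecise date costs less than losing the event.

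**The case against.** The strongest case for leaving the row alone has four parts.

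- *It may never apply.* Responses go into a dedicated eCRF, investigators verify entries, and reasons for missing data are recorded (SAP 7.1, Protocol 12.2.6). This stands: zero cases is plausible, and then nothing changes.
- *Nothing is decided on it.* The primary endpoint is TEAEs, and PFS and DoR are descriptive. This also stands.
- *The cases will be visible.* The row has its own censoring reason, reasons are tabulated, and PFS events and censoring are listed. True, but this shows the cases without correcting the estimate.
- *Protocol 10.3 says missing values are not replaced by estimates.* That concerns the date. It does not turn a known progression into a non-event. The SAP also assigns dates elsewhere: partial deaths (4.1.9), undated AE onsets (10.2.1.3) and the back-dating analysis (7.3.2.3).

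The documents do not support several stronger readings that a reader might infer:

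- *With 20 at risk, one lost event moves the curve by 1/20 = 5 points, and late cases matter more.* 1/20 is the conditional increment. Without earlier censoring, S is 20/51 = 39.2%, so the step is 39.2% × 1/20 = 2.0 points, the same at any time. A larger step needs heavy earlier censoring, which the documents do not forecast.
- *A PD date lacking only its day falls into this row.* SAP 4.1.9 distinguishes partial from missing dates, and the row refers to a missing date. The absence of a rule for a partial PD date is a gap. Its treatment under this row is inference.
- *The participant is credited with event-free time after progression.* Follow-up stops at the last adequate assessment. The bias comes from the lost event.

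**Conclusion.** The point holds as an error in a stated rule. The row conflicts with its own table's lead-in, with Protocol 10.3.2.3 and with the event definition in SAP 7.3.2. It biases PFS and DoR upward whenever it is used, and no sensitivity analysis offsets it.

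The size is small and conditional: nil with no cases, and otherwise about 0.6 to 0.7 points on 12-month PFS and 1.1 to 1.3 points on 12-month DoR per case. These figures rest on assumed exponential times, an 80% share of PD among events and 29 responders. The 2.0-point PFS ceiling assumes no other censoring. One or two cases are well inside the confidence interval. No hypothesis test, decision rule or primary-endpoint result depends on it, so this is a low-priority correction that is worth making because it is cheap.

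**What to change.** Query the missing date with the site before database lock. If it cannot be recovered, change the outcome in that Table 6 row from censored to progressed. Date the event at the recorded date of the visit at which PD was assessed or, if there is none, at the next scheduled assessment after the last adequate one, using the convention already in SAP 7.3.2.3. State in the same row how a later dated death is handled, which Table 6 does not settle. Keep the present censoring as a sensitivity analysis for both PFS and DoR.

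The end-of-treatment record should not supply the date. It reflects a treatment decision, whereas Protocol 10.3.2.3 requires radiologically documented progression and SAP 7.3.2 dates it from the assessment.

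The cost is one table row, a few lines of programming and one extra sensitivity run per endpoint. The downside is an approximate event date, least precise after Cycle 25, when scans are yearly.

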7.3.2.3. Identification of 2 or More Consecutive Missing or Inadequate Tumor Assessments

If death or progression occurs after 2 or more consecutive missed or inadequate tumor assessments, then the event will be censored on the date of the last adequate tumor assessment.

In one of the sensitivity analyses for PFS, an event occurring after 2 or more consecutive missed assessments will be back-dated to the date of the next scheduled assessment. The date of the next scheduled assessment is the date of the last adequate tumor assessment plus the Protocol-specified time interval for assessments.

The strategy to identify participants with 2 or more missed tumor response assessments after a valid tumor response assessment and the censoring rule are shown in Table 7

Table 7: Censoring Rule for Events After 2 or More Consecutive Missed or Inadequate Tumor Assessments

Valid Tumor Assessment Occurring Between	Minimum Number of Days From Last Valid Tumor Assessment	Censoring Date
Enrollment until C3D1 – 1 day	114 days	Date of last valid tumor assessment
C3D1 until C5D1 – 1 day	114 days	Date of last valid tumor assessment
C5D1 until C7D1 – 1 day	142 days	Date of last valid tumor assessment
C7D1 until C10D1 – 1 day	171 days	Date of last valid tumor assessment
C10D1 until C12D28 – 1 day	182 days	Date of last valid tumor assessment
Cycle 13 through Cycle 25 – 1 day	182 days	Date of last valid tumor assessment
After Cycle 25	730 days	Date of last valid tumor assessment

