From Cycle 4 onwards, blood samples for tafasitamab anti-drug antibodies (ADAs) will be collected pre-dose on D1 of every other cycle until Cycle 12, i.e. Cycle 4, Cycle 6, Cycle 8, Cycle 10, Cycle 12.

Tafasitamab PK sample will be taken pre-dose and 30 min  $\pm$  15 min after the end of tafasitamab infusion.

10aTafasitamab PK samples will be taken pre-dose and 30 min  $\pm$  15 min after the end of tafasitamab infusion on C4D1 and afterwards pre-dose on D1 of every other cycle until Cycle 12, i.e. Cycle 6, Cycle 8, Cycle 10, Cycle 12.

PET-CT or PET-MRI should be performed at screening, at C12D28 ( $\pm$  4 days) and at EOT visit unless disease progression was already radiologically confirmed prior to the EOT visit. If progression/relapse is suspected on the basis of clinical symptoms, PET-CT or PET-MRI should be performed to confirm disease progression. PET/CT or PET-MRI from Cycle 25 onwards should be performed only if deemed necessary, and not more than once per year.

11aCT or MRI should be performed within 4 days prior to C3D1, C5D1, C7D1 and C10D1. From Cycle 13-24 CT or MRI should be performed approximately every 3 months  $\pm$  2 days from the previous scan. The first assessment during this phase will take place 3 months  $\pm$  2 days after C12D28. From Cycle 25 onwards: approximately once every year  $\pm$  2 weeks from the previous scan.

Repeat bone marrow biopsy only in those patients who had known bone marrow involvement at screening to confirm a CR. If repeat bone marrow biopsy is required to confirm CR, the assessment should be done at C3D15  $\pm$  1 day and/or within 15 days after C5D1, C7D1, C10D1 and C12D28. Bone marrow assessment from Cycle 13 to 24 approximately every 3 months  $\pm$  2 weeks from the previous assessment to be performed to confirm a CR only in those patients who had known marrow involvement at screening.

Tafasitamab infusions should be given after pre-medication administration 30–120 minutes prior to starting the infusion. For patients who do not experience any grade 2 or higher IRRs with their first four infusions, pre-medication at subsequent treatments may be omitted according to institutional treatment guidelines.

Regardless of the reason for study treatment discontinuation, patients will have a safety follow-up visit or phone call scheduled 90 days after the last dose of the study treatment.

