6.4.1. Treatment Cycles

Each treatment cycle will consist of 28 days. The treatment plan is outlined in Table 4.

Note: Each treatment cycle is 28 days.

Dose reductions of tafasitamab are not allowed during the course of the study. Unless contraindicated, tafasitamab treatment should continue even if the participant discontinues LEN.

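### SAP Table 7 puts on-time Cycle 5, 7 and 10 scans in the wrong row, so one missed scan is censored as two in PFS and DoR

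*SAP*

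**What the plan says.** SAP Table 6 (section 7.3.2.2) has a censoring row for "Death or progression after 2 or more missed assessments": the patient is censored at the last scan that documented non-progression. Table 8 (section 7.3.2.4) is consistent with this. A death without adequate assessment counts as an event unless two consecutive assessments were missed. For DoR, section 7.3.3.1 states: "The censoring rules for DoR will be the same as those for PFS".

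Table 7 (section 7.3.2.3) turns the rule into day counts. It finds the row in which the last valid assessment fell, then applies that row's minimum number of days:

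| Last valid scan falls between | Limit (days) |
|---|---|
| Enrolment and the day before C3D1 | 114 |
| C3D1 and the day before C5D1 | 114 |
| C5D1 and the day before C7D1 | 142 |
| C7D1 and the day before C10D1 | 171 |
| C10D1 and the day before C12D28 | 182 |

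The second row reads "C3D1 until C5D1 – 1 day".

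For timing, SAP 7.3.2.1 relies on "scans as per the schedule in Table 3 of the Protocol". Footnote 11a of that table says "CT or MRI should be performed within 4 days prior to C3D1, C5D1, C7D1 and C10D1". Footnote 11 says "PET-CT or PET-MRI should be performed at screening, at C12D28", with a window of ±4 days. Footnote 11a adds, for the scans after Cycle 12: "The first assessment during this phase will take place 3 months", ±2 days, after C12D28.

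**The concern.** Table 7 draws its boundaries at the Day 1 visits, while the scans belonging to those visits are done one to four days earlier. A C5 scan done exactly as the protocol asks is therefore dated before C5D1 and is treated as a C3-period scan. The C7 and C10 scans are shifted in the same way. Each takes a limit built for an earlier and shorter stretch of the schedule.

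If the limit is too short, the rule fires after one missed scan instead of two. A progression or death that should count is then removed and replaced by censoring at the last scan. Fewer events with earlier censoring generally raises the PFS and DoR curves. If patients who miss a scan tend to be doing worse (plausible, but not something the documents establish), the censoring is also informative.

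**Working it through.** **Inputs.** SAP 6.4.1: "Each treatment cycle will consist of 28 days". Scan windows come from footnotes 11 and 11a of protocol Table 3, and limits from SAP Table 7. I assume no cycle delays. Three months is taken as 91 or 92 days, with other values tested below.

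**Calendar.** CnD1 = 28 × (n − 1) + 1, so C3D1 = day 57, C5D1 = 113, C7D1 = 169, C10D1 = 253 and C12D28 = 336. On-time scan days are:

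- C3: 53–56
- C5: 109–112
- C7: 165–168
- C10: 249–252
- C12D28: 332–340

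**Reproducing the plan's limits.** Most equal the span from the scan at the start of the row to the next scan but one, plus a window allowance:

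- Baseline to C5: 112 + 2 = 114
- C3 to C7: 169 − 57 = 112; + 2 = 114
- C5 to C10: 253 − 113 = 140; + 2 = 142
- C7 to C12D28: 336 − 169 = 167; + 4 = 171
- C10 row: 182 = 2 × 91. The schedule itself gives 83 + 91 = 174, or 176 with a 2-day window.

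So 142 and 171 are the limits for the C5 and C7 scans.

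**Gap after one missed scan against the limit actually applied.** Gap = day of the second scheduled scan − day of the last scan. The smallest gap uses the latest last scan and the earliest second scan; the largest uses the reverse.

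| Last scan | Missed | PD found at | Gap | Limit applied | Excess |
|---|---|---|---|---|---|
| C5 (109–112) | C7 | C10 (249–252) | 137–143 | 114 | 23–29 |
| C7 (165–168) | C10 | C12D28 (332–340) | 164–175 | 142 | 22–33 |
| C10 (249–252) | C12D28 | C12D28 + 91 or 92 (425–430) | 173–181 | 171 | 2–10 |

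All date pairs in all three rows are at or above the limit, so 100% are censored with one scan missed.

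**Length of three months (C10 row only).** At 89, 90, 91 or 92 days, 100% of pairs reach the limit. At 84 days, 30% do.

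**C3 scan.** Both candidate rows say 114, so the shift changes nothing.

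**Deaths.** A C5 scan on days 109–112 plus 114 gives days 223–226. From day 226, any on-time C5 scan is past its limit, yet the C10 window does not open until day 249. A death on days 226–248 with only C7 missed is censored back to days 109–112.

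**Shift in time.** The event becomes censoring 114 to 181 days earlier: 114 / 30.4375 = 3.7 months and 181 / 30.4375 = 5.9 months.

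**Effect of correcting the row.** With every row starting at CnD1 − 4 days and the limits left as they are, pairs at or above the limit fall to 3/16 (19%) for C5, 14/36 (39%) for C7 and 0% for C10. With limits of 144, 176 and 182 they fall to 0% for all three, because the largest gaps are 143, 175 and 181.

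**The case against.** **Table 7 may mean nominal visits.** SAP 4.1.7 uses the eCRF visit for by-visit parameters. If Table 7 rows follow the nominal scan visit, the C5, C7 and C10 scans receive 142, 171 and 182. It can also be said that 171 equals day 336 minus day 165, so it fits a pre-visit C7 scan as well as one on C7D1. But section 4.1.7 governs by-visit summaries, and Table 7 is worded in dates with boundaries one day before a visit. A programmer following the text gets the wrong row. Either derivation of 171 makes it the C7 scan's limit, which that scan does not receive. If nominal visits are intended, the table must say so.

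**A sensitivity analysis exists.** SAP 7.3.2.5 counts these PFS events, and censoring reasons are tabulated. This partly stands: the PFS events are not lost from every analysis. But that analysis uses the same flag and back-dates the events to the next scheduled scan, so single-miss events would be wrongly back-dated. The only sensitivity analysis that section 7.3.3.3 specifies for DoR uses the per-protocol set.

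**The death example is restricted.** A patient who stopped treatment would usually have an end-of-treatment scan, which resets the clock. This stands. The example applies to deaths on treatment or before that visit.

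**The C10 case is narrow.** This stands. It exceeds the limit by 2–10 days and fails mostly if three months is read as 84 days.

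**A scan on Day 1 itself takes the right row.** True, if the protocol window is read to include Day 1; the four days before it do not.

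**The number affected is unknown.** This stands. About 51 patients are planned. An affected patient must miss exactly one of three scans, have no valid unscheduled scan, and have the event in a limited period. PFS and DoR are secondary and descriptive.

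**Conclusion.** The concern holds. As written, Table 7 applies the two-missed-scans censoring after one missed scan for every on-time combination that starts from a C5 or C7 scan, by 22 to 33 days. It does the same from a C10 scan, by 2 to 10 days, when three months is 91 or 92 days. This contradicts the SAP's own definition in Tables 6 to 8 and carries over to DoR. It assumes planned 28-day cycles without delay and rows read as dates.

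The likely direction is upward for both endpoints. The size in terms of median PFS or DoR cannot be derived from the documents, although in about 51 patients a few lost events can move a Kaplan-Meier curve. Because the endpoints are secondary and untested, this should be corrected but does not threaten the primary safety objective.

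**What to change.** Select the Table 7 row by the nominal scan visit (C3, C5, C7, C10, C12D28, then each three-monthly scan) and say so in the table. Alternatively, start each row at least 4 days earlier, for example from C5D1 − 4 days to C7D1 − 5 days.

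In either case, set each limit above the longest on-time gap to the second following scan. For C5, C7 and C10 that means more than 143, 175 and 181 days, for example 144, 176 and the existing 182. Because the column is a minimum, a limit equal to the longest gap would still flag it. The C3 limit has the same small shortfall (day 168 − day 53 = 115 against 114) and can be raised to 116 in the same edit.

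There is a minor trade-off. With any fixed day limit, an event just after a second missed scan window can still be counted. For example, a last scan on day 112 with C7 and C10 missed and death on day 254 gives a gap of 142, below 144. Counting missed scheduled scans directly would avoid this.

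The cost is one SAP table edit and one derivation line, made before database lock, with no new data. PFS and DoR may look slightly less favourable.

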7.3.3.3. Sensitivity Analyses

The DoR endpoint will be analyzed using the PPS as a sensitivity analysis to the FAS.

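### SAP Table 7 does not implement the SAP's own rule on missed scans: some PFS and DoR events are censored when only one scan, or none, was missed

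*SAP*

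**What the plan says.** SAP 7.3.2.3 and SAP Table 6 (7.3.2.2) censor a progression or death at the last adequate scan if two or more assessments in a row were missed or inadequate. SAP Table 6 otherwise counts progression between scheduled assessments as an event, and likewise "Death between response assessments". SAP Table 7 identifies the affected patients by a minimum number of days since the last valid scan. The limit depends on the calendar interval in which that scan fell: 114 days for a scan before C3D1, 114 again for "C3D1 until C5D1 – 1 day", then 142, 171 and 182, 182 for "Cycle 13 through Cycle 25 – 1 day", and 730 after Cycle 25.

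SAP 7.3.2.1 takes the scan schedule from Protocol Table 3. Footnote 11a there states "CT or MRI should be performed within 4 days prior to C3D1, C5D1, C7D1 and C10D1". Footnote 11 adds a PET scan at C12D28 ± 4 days. In Cycles 13 to 24 scans follow about every 3 months ± 2 days, and then "From Cycle 25 onwards: approximately once every year", ± 2 weeks, counted from the previous scan.

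SAP 7.3.3.1 applies the PFS censoring rules to DoR. For PFS, SAP 7.3.2.5 plans a sensitivity analysis in which an event after missed scans "will be considered an event and back-dated to the date of the next scheduled assessment". For DoR, SAP 7.3.3.3 says only: "The DoR endpoint will be analyzed using the PPS as a sensitivity analysis to the FAS".

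**The concern.** A day limit is a valid stand-in for two missed scans only if it exceeds the longest gap a patient can show after missing one. Table 7 fails this in two places.

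- **Change to yearly scans.** The 182-day limit covers every scan up to Cycle 25, but the interval after the last of these is a year.
- **Row boundaries.** Rows start on Day 1 of Cycles 3, 5, 7 and 10, while the scans are due in the days up to Day 1. A compliant scan done early takes the previous row's shorter limit.

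Real events would then be removed from the PFS and DoR curves and tabulated as following missed scans that were not missed. Late DoR is the most exposed: it has no sensitivity analysis on censoring, and Appendix A Table 2.3.2 varies the response requirement instead.

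**Working it through.** **Inputs.** Cycles are 28 days (Protocol Table 1). With C1D1 = day 1: C3D1 57, C5D1 113, C7D1 169, C10D1 253, C12D28 336, C25D1 673, C26D1 701. A month is 30.4375 days (SAP 4.3.3), so 3 months is 91.3 days; 84 days (three cycles) is tried as an alternative.

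**Reproducing Table 7.** Placing each scan on the Day 1 that opens its row and measuring to the second-next scan:

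- C1D1 to C5D1: 112 + 2 = 114
- C3D1 to C7D1: 112 + 2 = 114
- C5D1 to C10D1: 140 + 2 = 142
- C7D1 to C12D28: 167 + 4 = 171
- Quarterly: 2 × 91 = 182; yearly: 2 × 365 = 730

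The C10D1 row also shows 182, although C10D1 to the first quarterly scan is 427 − 253 = 174 days. The early rows therefore look built for nominal scans, while their labels are calendar intervals.

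**Part (a): change to yearly scans.** Quarterly scans fall on about days 427, 519 and 610. The next quarter, day 701, is already in Cycle 26, so on the literal schedule the next scan is due at 610 + 365 = day 975.

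- Allowed gap: 365 ± 14, plus the 2-day window on the last quarterly scan: 349 to 381 days, against a limit of 182.
- Censoring starts at 610 + 182 = day 792. A death from then until the yearly scan, or a progression found at that scan, is censored with no scan missed.
- With 84-day quarters (420, 504, 588, 672) the next scan is about day 1037; the gap is again 365 ± 16.
- After the day-519 scan, censoring starts at day 701 with only the day-610 scan missed. The gap to the yearly scan is 456 ± 16, at most 472.

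**Part (b): row boundaries.** The last scan is done 1 to 4 days before Day 1, one scan is missed, and the next is on time.

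| Last scan | Days | Limit applied | Next on-time scan | Gap | Day pairs censored |
|---|---|---|---|---|---|
| C5 | 109–112 | 114 | C10, 249–253 | 137–144 | 20/20 |
| C7 | 165–168 | 142 | C12D28, 332–340 | 164–175 | 36/36 |
| C10 | 249–252 | 171 | First quarterly, 425–429 | 173–180 | 20/20 |

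With 84-day quarters the C10 case becomes 418–422, gap 166–173, 6/20. Including scans done on Day 1 itself, the counts are C5 20/25, C7 37/45 and C10 20/25 (6/25 at 84 days). For C3 to C7, 6/25 pairs reach 114.

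**Rows missing.** Day 336 (C12D28) lies between two rows. Read literally, Cycle 25 (days 673–700) has none.

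**Illustration for DoR (assumptions, not trial data).** Take 0.575 × 51 ≈ 29 responders, response at the C3 scan, all scans done, progression found at scans, and exponential DoR. The medians are 43.9, 26.1 or 15.0 months: the L-MIND estimate and lower confidence limits in Protocol 3.3.2 and 3.5.2. The day-610 scan is (610 − 57)/30.4375 = 18.2 months after response; the day-975 scan is 30.2. S(t) = exp(−ln 2 × t / median). Censoring every progression found at day 975 holds the curve at S(18.2).

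| Median | True S(30.2) | Under Table 7, S(18.2) | Difference | × 29 |
|---|---|---|---|---|
| 43.9 | 0.62 | 0.75 | 0.13 | 3.7 |
| 26.1 | 0.45 | 0.62 | 0.17 | 4.9 |
| 15.0 | 0.25 | 0.43 | 0.18 | 5.3 |

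If all progressions are found clinically, only those from day 792 (month 24.1) to day 975 are affected: 29 × [S(24.1) − S(30.2)] ≈ 1.8, 2.3 and 2.3.

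Simulation (20,000 responders per scenario) agrees: 4 to 5 affected if all progressions are found at scans, 2 to 4 if half or all are found clinically. With a 26.1-month median and scan detection, the DoR median reads as not reached at 3 years instead of 30.3 months; with half found clinically it reads 30.8 to 39.5. With 43.9 months and scan detection it is not reached either way, and with 15.0 it does not change. DoR at 24 months moves by 0 to −2 points, so the bias is not strictly one-way.

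**The case against.** The strongest points on the other side:

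- **Nominal visits.** SAP 4.1.7 uses the eCRF visit for by-visit summaries and adds no date-based windows. Applied to Table 7, an early C5 scan would get 142 days and part (b) would shrink to boundary cases of a few days. But that section governs summaries by visit, and Table 7 sets its rows by calendar day. The intent is plausible; the text does not say it.
- **Reading of footnote 11a.** If a scan near day 701 is expected, one scan has been missed by day 792 and the second is due about day 1066. The claim that no scan was missed then falls, but an event after one missed scan is still censored. A patient scanned on day 701 would be in the 730-day row, so the DoR illustration depends on the literal reading.
- **Back-dating.** If the schedule is clear, so is the interval. That is fair on the literal reading, but the last scan lies in the quarterly phase. A programmer could use day 701 or day 975.
- **Size.** The 13 to 18 points apply at month 30, beyond the example timepoints in SAP 7.3.3.2, which end at 24 months. They assume that all responders are still scanned and all progressions are found at scheduled scans. The day-pair fractions are not patient rates. All this stands.
- **Weight.** These are descriptive secondary endpoints. The primary safety endpoint and the dose recommendation are untouched, and PFS has a sensitivity analysis that counts these events. This also stands and limits the severity, but it does not remove the contradiction.

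**Conclusion.** The concern holds. Table 7 censors events that the rule in SAP 7.3.2.3 and SAP Table 6 would count. For the last scan before Cycle 25, the 182-day limit is about half the 349 to 381 days to the next on-time scan. This rests on the literal reading of footnote 11a and holds whether a quarter is 91 or 84 days. For early C5 and C7 scans, one missed scan always triggers censoring at the next on-time scan; for C10 it does so in all day pairs at 91 days and 30% at 84.

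Part (a) leaves the PFS median and the listed PFS landmarks to 24 months essentially unchanged. It distorts the later PFS tail, DoR after about month 18, and the table of censoring reasons. The number of patients affected cannot be derived from the documents; the DoR figures are an illustration under the stated assumptions. It should be corrected before the final analysis.

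**What to change.** 1. Assign each scan to its nominal visit. For both PFS and DoR, censor only if two or more protocol scan windows (footnotes 11 and 11a) closed without an adequate assessment between the last adequate scan and the event.
2. State that the back-dating interval after the last scan before Cycle 25 is the yearly one.
3. Add to DoR the back-dated sensitivity analysis already planned for PFS.
4. If day limits are kept, index them by nominal scan and censor only above them:
   - C3 116, C5 144, C7 175, C10 180
   - C12D28 about 189 (186 to 192 depending on how 3 months is counted)
   - a quarterly scan followed by two more, about 187
   - the second-to-last quarterly scan (day 519), about 472
   - the last scan before Cycle 25, about 746 to 759
   - yearly scans, about 744 to 759

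   Add rows for C12D28 and Cycle 25.

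Counting windows is preferable, because the approximate limits depend on how a quarter and the window tolerances are counted. The cost is one revised SAP table, one extra DoR output and minor reprogramming, with no new data. Late PFS and DoR estimates may come out slightly less favourable.
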